7.3.3 Criteria for Randomization

Eligible subjects will be rechecked at the time of admission to the study center (Day -1).

Results of the procedures performed on Day -1 as detailed Section 9.1.1, must be available prior to randomization. All inclusion and exclusion criteria will undergo a final verification before randomization.

7.3.4 Criteria for Subject Withdrawal from trial:

Subjects can be withdrawn from the study, as per the Principal Investigator's judgment, for the following reasons:

In case continuous participation in the trial is detrimental for subject's health, as per Investigator's judgment.

1. Hypertension signs and symptoms which require pharmacological treatment.
2. Syncope or shock.
3. Severe adverse reaction.
4. Serious Adverse Event.
5. Concurrent diseases or concomitant treatments not allowed by the protocol.
6. Lack of discipline.
7. Lack of compliance with the diet.
8. Lost of two samples within absorption period or near to the C_{max} .
9. If vomit occurs within therapeutic dosing interval, research subject should be withdrawn from the study and removed from the statistical analysis.

10. If any of the participant subject, during wash-out period, takes alcoholic beverages, smokes tobacco, has xanthenes containing beverages or food (coffee, tea, cacao, chocolate, mate, coke drinks, etc.) grapefruit, grapes or citrus, or grilled food (charcoal) within 24 h prior to the recruitment in the admission phase, or using any drug known by affecting the study.
11. Subjects with positive results to the drugs screening such as: amphetamines, benzodiazepines, cocaine, metamphetamines, morphine and tetrahydrocannabinoids.
12. Positive pregnancy test (qualitative or quantitative) following the study drug dosing.
13. All cases where the Principal Investigator judges as lack of compliance to the protocol or which may risk final results.

7.4 Start-up Criteria for Study Treatment

- All women of childbearing potential should test negative for pregnancy qualitative and quantitative test at day -1 of each treatment period.
- All subjects must have negative result for oral alcohol screening at SCR and at the beginning of each visit (day -1 for treatment period) and drugs of abuse (opioids, barbiturates, cocaine and its metabolites, amphetamines, metamphetamines, morphine, cannabinoids, benzodiazepines and tricyclic antidepressants), throughout the screening period and start of each one of the visits (day -1 for each treatment period).

7.5 Study Subject Withdrawal

Participant subjects in the study are free to withdraw from the study at any time and they will only be asked to give the reason of their withdrawal. An end of study examination must be performed if the subject has received at least one active drug as describe in section 8.2.7. Withdrawal reason should be documented in the medical chart in the case report form, if known. Study drug assigned to the dropped subject cannot be assigned to another subject. Subjects who withdraw after at least one IMP administration will not be replaced.

7.5.1 Withdrawal from the study

A subject must be withdrawn from the study for any event which might risk subject's safety. In the event pregnancy tests during subjects' admission are positive, their participation will be stopped immediately (for further procedure in case of pregnancy see section 8.5.2).

A subject should be withdrawn from the study in case of any of the following:

- Voluntary subject's withdrawal.
- Lost to follow-up.
- Participation in another investigational study.

7.6 Study termination

The clinical study can be finished or stopped early as per health authorities' request, in case of new safety or efficacy information posing a unfavorable risk - benefit for study subjects. The Sponsor may end the study in case it is no longer justified from the medical or ethical point of view; due to poor enrollment, due to the stop of the study drug's clinical development, withdrawal of the study drug or comparator from the market due to safety reasons.

Health Authorities, Independent Ethics Committee (IEC) and Investigational Committee (IC) will be informed about this cancellation as per the applicable regulations.

- ✚ This study can be stopped temporarily or definitively as per the Sponsor, Principal Investigator, or Ethics and Investigational Committee according the Ministry of Health's guidelines.
- ✚ Reasons can be several, among others, frequency and type of adverse events which lead to a considerable number of subjects to abandon the study; new information about the drug which affect directly subjects' safety or study conduct; or based on the Ethics and Investigational Committee, Investigational Committee and Ministry of Health's decision.
- ✚ In case of temporal or early termination, research subjects will be immediately informed and an appointment will be schedule to let them know the definitive decision about the study course. In case of definitive termination, the Principal Investigator will inform the study subjects about this decision and will determine the withdrawal procedures to be performed.
- ✚ If termination is due to the Sponsor or Principal Investigator's decision, decision between both of them should be documented in writing, providing the Ethics and Investigational Committee, the Investigational Committee and Ministry of Health with a detailed explanation about the temporary or definitive termination.
- ✚ Study drugs will be secured and kept, and will be disposed (return or storage) as agreed with the Sponsor.

7.7 End of Study Definition

The end of the trial is defined by the last contact with the last subject who participated in the trial (last subject last visit).

8 Investigational Drug and Other Drugs Used in the Study

1. Test drug: Fixed combination for Metformin/Gliclazide.
2. Reference drug: Concomitant dosing of Metformin + Gliclazide
3. Reference drug: Dosing of Metformin alone.
4. Reference drug: Dosing of Gliclazide alone.

8.1 Investigational Drug Description

Study Sponsor will provide drugs to be administered to the subjects in each of the study visits.

- + International non-proprietary name: Metformin/Gliclazide.
- + Reference drug: Dabex[®] XR.
 - Dosage form: tablets
 - Quali-Quantitative Formula: each tablet contains 1000 mg of Metformin hydrochloride.
 - Manufacturer: Merck KGaA
 - Distributor: MERCK, S. A. de C. V.
 - Marketing Holder: MERCK, S. A. de C. V.
- + Reference drug: Diamicon MR[®].
 - Dosage form: extended release tablets
 - Quali-Quantitative Formula: Each tablet contains 30 mg of Gliclazide.
 - Manufacturer: Les Laboratoires Servier Industrie
 - Distributor: Beckman Laboratories de México, S. A. de C. V.
 - Marketing Holder: Beckman Laboratories de México, S. A. de C. V.
- + Test drug: Metformin 1000 mg/Gliclazide 30 mg MR.
 - Dosage form: tablets
 - Quali-Quantitative Formula: Each tablet contains Metformin 1000 mg/Gliclazide 30 mg MR.
 - Manufacturer: Merck, SA, Brazil.
 - Distributor: Merck, SA, Brazil.
 - Marketing Holder: Merck, SA, Brazil.
- + Dosage: Metformin 1000 mg/Gliclazide 30 mg MR.
 - Treatment 1: dosing of fixed combination of Metformin 1000 mg/Gliclazide 30 mg MR (one tablet).

Drug's name: Metformin/Gliclazide
Protocol number EMR200763-003/ BD1412-62CEC

- Treatment 2: concomitant dosing of Metformin 1000 mg/Gliclazide 30 mg (two tablet.)
- Treatment 3: dosing of Metformin 1000 mg (one tablet.)
- Treatment 4: dosing of Gliclazide 30 mg (one tablet.)

Test drug should be imported as per the following quantities and specifications:

Description: Fixed combination tablet of Metformin 1000 mg/Gliclazide 30 mg.

Quantity required for each stage of the research: 11 tablets.

60 tablets for the study.

220 tablets for the finished product analysis and dissolution profile:

60 tablets as retention sample.

Manufacturer: Merck KGaA

Products importer:

Merck S.A. de C.V.

PPD 

PPD 

Merck LATAM

PPD 

8.2 Dosage and administration

After 10 hours of fasting conditions the dose to be used in the study will be the fixed Metformin XR 1000 mg/Gliclazide MR 30 mg combination as single dose of the test product or the individual reference products as appropriate for each period.

8.3 Randomization to treatment groups

Once it is confirmed that all inclusion criteria and none exclusion criteria have been met, subjects will be randomized to one of four treatment sequences. Randomization of each subject to a treatment sequence will occur prior to dosing on Day 1. The Investigator or delegate will allocate from the treatment kit stock (numbered 101-140 the next available treatment kit in a sequential, chronological order starting with the lowest number. Randomization will be based on a unique randomization list.

The Principal Investigator will perform the randomization list before the Day 1, the list will be generated from the Web Site Randomization.com (<http://www.randomization.com>). Once obtained, the format PPD [REDACTED] "Treatment Sequence" will be developed which will review Quality Management according to the standard operation procedure, code: PPD [REDACTED], randomizing a clinical study of interchangeability and comparability

An additional set of 12 treatment kits for possible replacers will be provided. There will be 3 treatment kits per treatment sequence. Replacement kit numbers will be 987 to 999. The pharmacist will assign the open-label replacement kit according to the treatment sequence of the originally assigned kit.

8.4 Selection and Dosing Schedule for Dosing for Each Subject

Forty male and female subjects will be included in this trial. Both sexes will be included with a minimum proportion of 30% for each sex at least 12 females and at least 12 males.

Ten subjects will be randomized to each treatment sequence with a minimum proportion of 30% for each sex in each treatment sequence.

The administration of the test or reference drug will be held at morning (about 08:00 h) after the fasting period (minimum eight hours) and follow the randomization list. It shall be recorded in the Case Report Form the current time of drug administration

During each period one of the four treatments will be dosed for all subjects from 08:00 till 08:14 h, in 8 groups of 5 subjects, with a 2-minute gap among each group for dosing and each one of the activities. Group's distribution can be changed due to operational reasons, as long as there is no impact in the study results.

Group's distribution, subjects and dose schedules are shown in the following table.

Dosing scheme

Group	No. of subjects	Dosing schedule
A	01, 02, 03, 04 and 05	08:00 h
B	06, 07, 08, 09 and 10	8:02 h
C	11, 12, 13, 14 and 15	8:04 h
D	16, 17, 18, 19 and 20	8:06 h
E	21, 22, 23, 24 and 25	8:08 h
F	26, 27, 28, 29 and 30	8:10 h
G	31, 32, 33, 34 and 35	8:12 h
H	36, 37, 38, 39 and 40	8:14 h

8.5 Concomitant therapies and drugs

Subjects are not allowed to take any drug within 7 half-lives (14 days) prior to the study drug dose. This restriction should be followed during the 4 study periods and the wash-out periods among doses.

All concomitant drugs taken by the subjects during the study, starting as per the informed consent signature should be appropriately recorded in the CRF, stating the name, dose and indication for each drug. Non-pharmacological interventions or any other intervention should be recorded in the CRF.

8.5.1 Allowed Drugs

Concomitant use of drugs is not allowed, unless those prescribed for adverse events and to protect subjects' wellbeing who will be allowed to continue in the study as per the Principal Investigator's judgment. This should be justified in the medical chart.

8.5.2 Forbidden Drugs

Subjects who take any other drug, prescribed or over the counter drugs 2 weeks before the study drug dose and for which at least seven elimination half-lives had not elapsed, including multi-vitamins and herbal products (e.g., St. John's Wort) in addition to ASA and oral contraceptives for women.

8.5.3 Other Interventions

Subjects who have been exposed to agents known as inducers or inhibitors of liver enzymatic systems, who have taken drugs potentially toxic within 30 days prior to the study start-up, who require any drug throughout the study, who have history of gastrointestinal tract surgery which might affect gastrointestinal absorption and/or motility are not allowed to participate in the study.

8.5.4 Special Warnings

In case of adverse events, medical staff will provide medical care required depending on the adverse event occurred. In case of severe eventuality, which requires hospital admission, the Principal Investigator or medical staff on duty will request the transfer of the subject to the agreed hospital and will contact the external ambulance service, according to the standard operating procedure, code: PPD Management of clinical eventualities.

8.5.5 Management of Specific Adverse Events or Adverse Drug Reactions

In case of adverse events, medical staff will provide immediate medical care required depending on the adverse event occurred. The Principal Investigator will decide the subsequent management, according to the standard operating procedure, code: PPD Management of clinical eventualities.

8.6 Investigational Drug Packaging and Labelling

Diabex XR[®] de Merck, S.A. de C.V., México

Reference drug will be provided by the Sponsor, in commercial dosage form (original primary and secondary packaging).

Drug will be stored in a closed package, identified with an external label containing study code and, if applicable, an internal label containing the study code, batch number and expiry date as minimum. Drug will be stored according to the product's needs.

Reference product will be given orally at a dose of 1000 mg (one tablet) of Metformin XR, given with 250 mL of water. Single dose.

Diamicron[®] MR, Laboratorios Servier México

Reference drug will be provided by the Sponsor, in commercial dosage form (original primary and secondary packaging or prototype).

Drug will be stored in a closed package, identified with an external label containing study code and, if applicable, an internal label containing the study code, batch number and expiry date as minimum. Drug will be stored according to the product's needs.

Drug's name: Metformin/Glicazide
Protocol number EMR200763-003/ BD1412-62CEC

Reference product will be given orally at a dose of 30 mg (one table) of Gliclazide XR, given with 250 mL of water. Single dose.

Fixed dose combination of MR Metformin 1000 mg and Gliclazide 30 mg from Merck, S.A., Brazil

Reference drug will be provided by the Sponsor, in commercial dosage form (original primary and secondary packaging or prototype).

Drug will be stored in a closed package, identified with an external label containing study code and, if applicable, an internal label containing the study code, batch number and expiry date as minimum. Drug will be stored according to the product's needs.

Test product will be given orally at a dose of Metformin 1000 mg/Gliclazide 30 mg (one tablet) with 250 mL of water. Single dose.

All study drugs will be packaged and labeled according to the applicable standards and directives from Good Manufacturing Practices.

8.7 Preparation, Management and Storage of Study Drug

Test and reference drugs will be received at the PPD [REDACTED] by the Pharmacy Responsible or by the designated staff, as per the standard operating procedures, code: PPD [REDACTED] Receipt, use, balance and final disposition of the study drug. Once drugs have been identified, they will be kept by the clinical unit until they are administered to the subjects.

Acceptance criteria for test and reference drugs.

- ✚ Complete documentation:
 - ✓ Certificate of Analysis.
 - Dosage units.
 - Content assessment.
 - ✓ Letter of Good Manufacturing Practice compliance for test and reference drug.
 - ✓ Copy of the invoice for the reference drug.
- ✚ Test drug with label compliant with the minimum requirements from NOM-072-SSA1-2012, Labelling of Drugs and Herbal Remedies.
- ✚ Enough quantity of test and reference drug.

- ✚ Expiry date not due at the moment of use in the clinical study.
- ✚ Test and reference drug in good physical conditions.

Rejection criteria for test and reference drugs.

- ✚ Blister which have been tampered.
- ✚ Drug received out of the storage or transportation specifications.
- ✚ In case primary package is damaged.

Drug should be stored in a safe, dry, and locked cabinet at a temperature not higher than 25 °C according to the label information.

8.8 Study Drug Accountability

The Sponsor will ship enough quantities of the test and reference product to conduct the study and keep some as "retention samples" to the PPD [REDACTED]

The Principal Investigator, Pharmacy Responsible or designated staff at the PPD [REDACTED] will be in charge of dispensing the number of required doses the day of the study as well as of keeping an inventory of used and stored doses as retention samples, according to the standard operating procedure, code: PPD [REDACTED]. Receipt, use, balance and final disposition of the study drug.

8.9 Assessment of Study Drug Compliance

Throughout dosing period, dose, full intake and time will be checked and recorded in the appropriate forms, according to the standard operating procedure, code: PPD [REDACTED]. Preparation and administration of drugs in clinical trials of interchangeability and biocomparability; PPD [REDACTED]. Randomization in an interchangeability and biocomparability clinical study

A subject is compliant with the treatment only if he/she completes all study periods.

8.10 Method of Blinding

Not applicable, this is an open-label trial.

8.11 Emergency Unblinding

Not applicable, this is an open-label trial.

8.12 Overdose treatment

Overdose is defined as any dose higher than the highest daily dose included in the clinical protocol or foreseen for a subject recruited in the study.

Even though this does not meet criteria for serious adverse event, any overdose should be recorded in the study drug section of the CRF and medical chart. It should be reported to the *National Center of Pharmacovigilance* (CNFV) from the *Federal Commission for the Protection Against Sanitary Risks* (COFEPRIS), according to the standard operating procedures, code: PPD [REDACTED] Adverse event reporting in clinical and bioavailability studies and the Mexican Official Standard for Setting-up and Operations of Pharmacovigilance in Mexico, NOM-220-SA1-2012 and following procedure listed in section 8.5.1. If the overdose caused a SAE, it has to be reported immediately the sponsor according to the section 10.1.1.2.

The study medication will be prepared and administered under the supervision of the Principal Investigator, once administered the study drug, the drug will secure again in the area of pharmacy, which will be restricted for access.

Gliclazide overdose:

Study drug overdose may lead hypoglycemia.

Moderate symptoms of hypoglycemia without unconsciousness or neurological sign should be fully corrected by means of glucose administration. Observation and strict control should continue until the Principal Investigator is sure that the subject is not at risk anymore.

Severe hypoglycemic reactions such as coma, seizures and other neurological disorders are possible and they should be managed as a medical emergency which requires immediate hospital admission.

During the study all subjects will have their finger stick blood glucose measured (see section 8.5) and will be given 10 mL of concentrated glucose solution (20 to 30 %) within 1 or 2 hours following the dose. Glucose solution charges are not limited to these two occasions. If hypoglycemia symptoms occur, additional glucose solution can be given. The concentrated glucose solution (20 to 30 %) should be given slowly, preferably through a small bore needle into a large vein, to minimize venous irritation.

Subject should be closely controlled, based on his condition following that episode and the Principal Investigator will make a decision whether subsequent control is necessary.

Metformin overdose:

Hypoglycaemia has not been seen with Metformin doses of up to 85 g, although lactic acidosis has occurred in such circumstances.

High overdose of Metformin or concomitant risks may lead to lactic acidosis. Lactic acidosis is a medical emergency and must be treated in hospital. The most effective method to remove lactate and metformin is haemodialysis.

Symptoms and Management of overdose of the combination drug product (Metformin and Gliclazide):

Symptoms

No data are available with regard to overdose of the fixed-dose combination product.

Symptoms of a Metformin overdose

High overdose of metformin or concomitant risks may lead to lactic acidosis. Lactic acidosis is a medical emergency and must be treated in hospital.

Symptoms of a Gliclazide overdose

An overdose of sulphonylureas may cause hypoglycaemia.

Management

Management of a Metformin overdose:

The most effective method to remove lactate and Metformin is haemodialysis.

Management of a Gliclazide overdose:

Moderate symptoms of hypoglycaemia, without any loss of consciousness or neurological signs, must be corrected by carbohydrate intake, dose adjustment and/or change of diet.

If hypoglycaemia coma is diagnosed or suspected, the patient should be given a rapid i.v. injection of 50 mL of concentrated glucose solution (20 to 30 %). This should be followed by continuous infusion of a more dilute glucose solution (10 %) at a rate that will maintain blood glucose levels above 1 g/L. Patients should be monitored closely and, depending on the patient's condition after this time, the doctor will decide if further monitoring is necessary.

Gliclazide is not dialyzable due to its strong binding to proteins.

Hypoglycaemia has not been seen with Metformin doses of up to 85 g, although lactic acidosis has occurred in such circumstances. High overdose of Metformin or concomitant risks may lead to lactic acidosis. Lactic acidosis is a medical emergency and must be treated in hospital. The most effective method to remove lactate and Metformin is haemodialysis (CCDS Metformin V7).

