9.1.2 Study periods

At the beginning of each period, a clinical assessment consisting of an examination by apparatus and systems will be made in order to check if the subject remains eligible for the study. Blood will be taken for pregnancy tests for women of childbearing potential and urine samples for drug screening. Oral alcohol test will also be performed.

Subjects should inform the medical staff in charge of the study conduct about any symptom they might have. Likewise, medical staff will question the subjects in every study period about symptoms occurred since recruitment in the first period, prior and following dosing. In case they report any, they will be provided with care and notes will be made in the appropriate documents.

During admission, subjects will be continuously monitored and an electrocardiogram will be performed pre-dose, during each discharge (48 h post-dose) and during the last outpatient sampling (168 h post-dose) at each visit.

During each admission, blood and urine samples will be taken from subjects for safety laboratory tests such as hematology, blood chemistry, prothrombin time (PT) and partial thromboplastin time (PTT) and urinalysis. Samples will be taken pre-dose (following 10-h fasting) and at discharge (48 h post-dose).

Glucose measurements will be performed: at each pre-dose and 4, 12, 24, and 32 h post-dose. Finger stick glucose measurement (Hematoglucotest) will be made at each pre-dose and 2, 4, 8, 12 and 24 h post-dose.

At the end of each period and at the last outpatient sample (sample 168.00 h post-dose) a clinical assessment will be made. It will consist of an interview, physical examination (oral cavity examination, lungs, heart, abdomen and other organs, if necessary in case of symptoms), vital signs measurement and follow-up of adverse events. Blood and urine samples will be taken for safety laboratory tests such as hematology; blood chemistry, prothrombin time (PT) and partial thromboplastin time (PTT); and urinalysis.

At the last visit for outpatient sampling (168.00 h post-dose) a clinical assessment will be performed consisting of an interview, physical examination (oral cavity examination, lungs, heart, abdomen and other organs, if necessary in case of symptoms).

Weight and height, and vital signs will be measured; and electrocardiogram and adverse events follow-up will be carried out. Blood samples will be taken for pregnancy tests for women of childbearing potential.

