9.4.2 Pregnancy and Exposure to Drugs in the Uterus

All pregnancies, with a conception date estimated during the period defined in section 9.5.1.3. will be recorded as AE in the appropriate CRF page/section. For female subjects and male subjects' female partners as AE or SAE depending on the outcome of the pregnancy. The Principal Investigator should inform immediately the Sponsor or designated person about any pregnancy using a Pregnancy Report Form which should be submitted according to the same procedure for SAE referred in section 9.4.1.10.

The Principal Investigator or designated person should follow-up, document and report all pregnancies outcomes, even if subjects were withdrawn from the study.

The Principal Investigator should inform the Sponsor or designated person about the outcome using the Pregnancy Report Form. In case of an abnormal outcome, the SAE Report Form will be used. In case subject, child/fetus experienced an event, the Parent-Child/Fetus Adverse Event Report Form will be used.

Any abnormal outcome should be reported immediately as described in section 8.4.1.4. All abnormal outcomes should be reported (the observation period comprises 45 days following the delivery).

In case of pregnancy during the study, the subject should be withdrawn and no further IMP has to be given. Sponsor or designated person should be immediately informed and follow-up should be made as aforementioned.

Uncontrolled diabetes during pregnancy (gestational or permanent) is associated with increased congenital abnormalities and perinatal mortality. The use of the combination drug Metformin and Gliclazide has not been studied in pregnant women.

A limited amount of data from the use of Metformin in pregnant women does not indicate an increased risk of congenital abnormalities. Animal studies with Metformin do not indicate harmful effects with respect to pregnancy, embryonic or fetal development, parturition or postnatal development.

With Gliclazide no teratogenic effects have been shown in animal studies, but lower fetal body weight was observed in animals receiving doses 25 fold higher than the maximum recommended dose in humans. No impairment of fertility was seen in a study with male and female rats.

When the patient plans to become pregnant and during pregnancy, it is recommended that diabetes is not treated with Gliclazide, but insulin should be used to maintain blood glucose levels as close to normal as possible.

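### Section 8.12 orders concentrated glucose for all subjects soon after dosing, but the supplied schedule and safety sections list glucose measurements only

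*Protocol*

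**What the plan says.** Section 8.12 of the protocol deals with overdose. Under its gliclazide sub-heading it says that during the study "all subjects will have their finger stick blood glucose measured (see section 8.5"), and that the same subjects "will be given 10 mL of concentrated glucose solution (20 to 30 %) within 1 or 2 hours following the dose". It continues: "Glucose solution charges are not limited to these two occasions". It then provides for symptoms separately: "If hypoglycemia symptoms occur, additional glucose solution can be given".

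The sections that staff would work from on the day read differently:

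- **9.2.1, Day 1.** The schedule runs hour by hour and includes small steps such as morning grooming and a drink of water. At 09:00 it lists a PK sample. At 10:00 it lists a PK sample and a finger-stick. No glucose administration appears. Sections 9.2.3, 9.2.5 and 9.2.7 apply the same schedule to periods 2 to 4.
- **9.1.2.** Measurements only: "Finger stick glucose measurement (Hematoglucotest) will be made at each pre-dose and 2, 4, 8, 12 and 24 h post-dose", plus blood glucose before the dose and at 4, 12, 24 and 32 h.
- **9.4.** The same measurements, again with no administration.
- **9.1.3.** A fast of at least 4 h after dosing, with breakfast from 12:00. Glucose is not mentioned.

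The text of Appendix 1 (blood sampling and meals) is not in the supplied protocol. Only its title appears in the contents list.

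**The concern.** Read as written, 8.12 gives a step to every fasting healthy volunteer, and three of the four treatments contain a sulphonylurea. The schedule does not carry that step. Staff working from the printed Day 1 list could leave it out, while staff working from 8.12 would give it.

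Section 8.12 is also unclear in itself. The timing is one or two hours, yet the next sentence speaks of two occasions, so one or two administrations are possible. The wording covers all subjects, but it stands under an overdose heading, which leaves some doubt about scope, including whether the metformin-alone period is covered.

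What is at stake is first subject safety, and then the reading of hypoglycaemia, which 9.4.1.7 makes the adverse event of special interest. A low value at 2 or 4 h means something different after glucose than without it. Unless administrations are timed and listed, the two cases cannot be told apart.

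**Working it through.** The point turns on consistency between sections. The protocol gives no figure to reproduce.

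**1. Is the instruction routine or only for symptoms?** Section 8.12 says all subjects, during the study, and counts the time from the dose. Glucose for symptoms is called additional, so the first administration does not depend on symptoms. The wording reads as routine, and only the heading points the other way.

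**2. Does the schedule contain it?** With dosing at 08:00 (last group 08:14, section 8.4), 1 h and 2 h after the dose are 09:00 and 10:00, up to 14 minutes later for the last group. Neither entry in 9.2.1 lists glucose administration. Both times fall inside the 4 h fast.

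**3. Does the cross-reference settle it?** Section 8.5 is now concomitant therapies and contains no glucose measurement. The number is probably left over from another numbering: 7.5.1 says "for further procedure in case of pregnancy see section 8.5.2", while "Pregnancy and Exposure to Drugs in the Uterus" is now 9.4.2. On that pattern 8.5 would be 9.4, which lists measurements only. Following the reference therefore does not answer the question.

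**4. How far apart are the readings?** Taking the percentage as weight by volume (an assumption):

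- One administration: 10 mL × 0.20 to 0.30 g/mL = 2 to 3 g.
- Two administrations per dosing: 4 to 6 g.

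Administrations outside symptomatic treatment, for a subject who completes all four periods:

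| Reading of 8.12 | Count |
|---|---|
| Overdose cases only | 0 |
| Gliclazide-containing periods only, one each | 3 × 1 = 3 |
| Gliclazide-containing periods only, two each | 3 × 2 = 6 |
| Every period, one each | 4 × 1 = 4 |
| Every period, two each | 4 × 2 = 8 |

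**5. Which glucose readings are exposed?** Post-dose readings per period, from 9.1.2:

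- Finger-stick at 2, 4, 8, 12 and 24 h: 5.
- Blood glucose at 4, 12, 24 and 32 h: 4. This agrees with the five glucose samples per period in 9.4.3, one of which is pre-dose.
- Firm total: 5 + 4 = 9.

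The 48 h chemistry sample is left out, because the protocol confirms glucose in that panel only where it describes eligibility tests (7.3.1).

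None of the 9 readings comes before 2 h. Three are taken up to the 12:00 breakfast: the 2 h finger-stick, the 4 h finger-stick and the 4 h blood glucose. All three fall at or after the 1 to 2 h window.

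**The case against.** The strongest reply is that silence is not contradiction. Sections 9.1.2 and 9.4 describe assessments, so measurements are what they would list, and Appendix 1 might carry the step. Part of this stands: none of the supplied sections forbids the glucose, and Appendix 1 could not be checked. But 9.2.1 is an itemised list of the day's actions, and an intervention for every subject belongs in it. Appendix 1 would also not necessarily resolve the count and scope questions inside 8.12.

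It can also be said that 8.12 largely answers itself, since two occasions means two and all subjects means all. That is the more natural reading. It makes the missing schedule entry more important, not less.

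A reader might infer more than the documents support:

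- **A conflict with the concomitant-drug rule.** Section 8.5.1 says "Concomitant use of drugs is not allowed, unless those prescribed for adverse events and to protect subjects' wellbeing". Glucose given as a safety measure can fall under the wellbeing clause, so this is not a conflict.
- **A breach of the fast.** Section 9.1.3 does not mention glucose, and 8.12 describes injection into a vein as the preferred way of giving it, so no oral intake is implied. The two sections need aligning, but neither breaks the other.
- **A clash with the 50 mL rapid injection elsewhere in 8.12.** That text concerns suspected coma, a different situation.
- **Distorted treatment comparisons.** There is one site, and each treatment appears once in each period across the four sequences. Giving glucose in one whole period and not in another would, before drop-out, touch all four treatments equally. Uneven use within a period could distort the by-treatment summaries in 9.10.3, but nothing in the documents directs it.
- **A biased bioequivalence result.** Nothing in the documents links this glucose to AUC or Cmax.
- **No record at all.** Section 8.5 already requires concomitant drugs, with name, dose and indication, and other interventions to be entered in the CRF. What it does not require is the clock time.

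**Conclusion.** The point holds as a gap between sections. Section 8.12 orders glucose for all subjects shortly after dosing. The supplied Day 1 schedule and the two monitoring sections contain only measurements, and the number of administrations is open. The scope is somewhat in doubt because of the heading, although the wording reads as routine.

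The readings run from 0 to 8 administrations per completing subject, and 3 of the 9 firm post-dose glucose readings in each period lie where the answer matters. The gram figures assume weight by volume. The conclusion that the schedule omits the step is limited to the supplied text.

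No size of effect on glucose is claimed. The consequence is a safety step that could be missed, and early glucose readings that cannot be interpreted without knowing what was given.

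**What to change.** The sponsor and investigator should reconcile sections 8.12, 9.1.2, 9.1.3, 9.2.1 and 9.4 (and Appendix 1, if it bears on this) into one instruction saying whether, to whom, when and how often glucose is given outside symptomatic treatment. That instruction should then appear in the Day 1 schedule, and the reference to section 8.5 should be corrected. Which clinical rule applies is for them to decide, and this review does not choose one.

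The clock time of each administration should be added to the CRF entry that 8.5 already requires, and listed by treatment beside the glucose readings. The SAP is written partly in the past tense. If dosing is already complete, the study report should state what was actually done and give the same listing from whatever times were recorded.

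The cost is a protocol clarification, one corrected cross-reference, one time field and one listing. It needs no added subjects, visits or samples.
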